As has been outlined in the Preliminary Results section of this proposal, *anti*-[¹⁸F]FACBC has been demonstrated to 1) have high sensitivity in the detection of recurrent prostate carcinoma though with suboptimal specificity in the prostate bed, and 2) the ability to differentiate prostatic from extraprostatic recurrence with high accuracy. *anti*-[¹⁸F]FACBC may thus have specific advantages for imaging recurrent prostate neoplasia within a clinical setting over conventional imaging. Yet, MR, especially with the addition of diffusion weighted imaging, has been reported in preliminary studies to provide high accuracy especially in the characterization of prostate bed recurrence. We hypothesize that utilization of a transmolecular approach combining synthetic amino acid radiotracer PET imaging with multiparametric MR has the potential to identify the presence and location of recurrent prostate carcinoma to a higher accuracy than either modality alone. **Therefore the most comprehensive manner to assess our hypothesis that PET-CT imaging with *anti*-[¹⁸F]FACBC in combination with multiparametric MR will lead to improved patient care resulting from detection of local and distant recurrent disease (Specific Aim #1) is to undertake a prospective clinical trial designed to address these issues.**

Secondary Aims

Aim 2. To determine mRNA differences between prostate carcinoma recurrent in the prostate bed and extraprostatic locations and to correlate any difference with quantifiable imaging biomarker data such as SUV for *anti*-[¹⁸F]FACBC PET-CT and ADC for MR.

Within the structure of the clinical trial (the same 25 patients) we will obtain sufficient tissue to perform mRNA sequencing on samples to exploit differences between the genetic profiles of recurrent prostate carcinoma in the prostate bed versus metastases. Since approximately 30% of patients with PSA > 4 ng/ml by our experience manifest with both prostate bed and nodal recurrence, we believe at least 8-10 patients in whom this comparison can be directly made will be available for analysis. This may also occur with lower PSA levels with faster DT. We will then correlate any differences in genotypic profile with imaging biomarkers from synthetic amino acid PET and MR, such as SUV and ADC.

Sub-aim 2a. To evaluate protein expression of previously identified amino acid transporters (AATs) that have been implicated in the uptake of *anti*-[¹⁸F]FACBC.

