Also within the context of the clinical trial of 25 patients, we will, whenever there is sufficient tissue, determine if candidate amino acid transport (AAT) proteins identified from data obtained in an earlier study (Project 1: P-50 ICMIC) are expressed. We will perform IHC analysis of up to 7 candidate AAT or co-transporters, specifically PAT 1, LAT1, LAT2, 4F2hc, and ASCT2, LAT3 and ASCT1 to understand if the AAT whose mRNAs are increased in malignant prostate carcinoma and correlated with *anti*-[¹⁸F]FACBC uptake are expressed at the protein level by IHC analysis.

Rationale for Aim 2 and Sub-aim 2a.

As has been outlined in the Preliminary Results section of this proposal, there is preliminary data in the literature of gene expression and mutational differences between primary prostate carcinoma cells and those prostate metastases [7-9] as well as between bone metastases and non-osseous metastases [8]. We propose within the context of this clinical trial to provide tissue to further understand these differences both in the ability of prostate carcinoma to transport and retain amino acids measured as uptake of *anti*-[¹⁸F]FACBC and expression characteristic as studied by multiparametric MR such as ADC parameters on DWMR and uptake and retention of Gadolinium. If we can determine that there are gene expression differences between malignancy confined to the prostate bed and those that are extraprostatic, we can correlate these differences to PET uptake and MR appearance. Furthermore, we may also be able to derive incidental genotypic information that could be exploited on subsequent unrelated experiments. In addition, we have preliminary evidence based on our earlier research that PAT1, LAT2 and ASCT2 as well as LAT1, xCT, LAT3 and ASCT1 were associated with malignancy. Out of the AATs that were associated with malignancy, PAT1 expression had the strongest correlation coefficient relative to *anti*-3-[¹⁸F]FACBC uptake [38]. We believe that a study such as this one provides an ideal opportunity to obtain both prostatic and extraprostatic tissue from the same patient in order to test these hypotheses using the patient as his own control.

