Our rationale for utilizing patients with PSA ≥ 4 is as follows. A total of 127 patients have been studied already in an R-01 study of the diagnostic performance of *anti*-3-[¹⁸F]FACBC versus conventional imaging. If the patients are stratified by PSA level as in the table below, 41/73 were positive in the prostate bed only, 25 in both prostate bed and lymph nodes, and 1 in lymph nodes only. Thus, in the 25 patients whom will be studied in this population,

approximately 23 will be expected to have disease in the prostate bed and approximately 9 will have disease in nodes, most of the latter will also have disease in the prostate bed. This should provide sufficient tissue for the above secondary aims. In addition, we have demonstrated that greater extraprostatic involvement will occur with shorter DT even at lower PSA levels. Thus the addition of PSA 2.0-3.99 ng/ml plus DT \leq 10 months is a reasonable method to increase recruitment while still acquiring tissue from extraprostatic involvement.

PSA group	<4 (n=54)	\geq 4 (n=73)	Total(n=127)
Prostate bed only (+)	27	41	68
LN only (+)	3	1	4
Both	8	25	33
Total	38	67	105

We hypothesize that by identification of disease recurrence in the prostate bed and extra-prostatic locations, we can exploit differences in mRNA analysis to correlate these differences to synthetic amino acid transport as well as MR parameters such as ADC mapping, and also better understand the relationship of AAT protein expression to *anti*-3- ^{18}F FACBC uptake. **Therefore the most comprehensive manner to obtain tissue to test our hypotheses is within the context of this prospective clinical trial.**

[figure not shown]
C1.0 Research Design and Methods (Aim 1)

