Upon completion of the study and/or after additional follow-up, each patient may be re-reviewed by the same Ground Truth Panel to determine if the predicted findings on *anti*-[¹⁸F]FACBC scan and MR individually and in tandem match those of clinical and pathologic findings especially in regard to the identification of prostatic versus extraprostatic recurrence. Also at that time uptake parameters will be reviewed. At no time this study will interfere with proper therapy as determined by the patient's physicians and the patient.

C2.0 Study Design and Methods (Aim2 and Sub Aim 2a)

Rationale. We hypothesize that *anti*-[¹⁸F]FACBC uptake is mediated by a LAT protein subtype or subtypes. However, the precise LAT subtype involved in all cases is unknown. We also further hypothesize that there are genotypic differences between recurrent prostate carcinoma cells confined to the prostate bed and those that are extraprostatic and that these differences can be explored via proper identification of candidate tissue via transmolecular imaging to be performed at termination of study or when sufficient tissue has been collected.

Experimental Design. To test the above hypothesis, we will compare mRNA expression of recurrent prostate carcinoma tissue within the prostate bed and extraprostatic. In addition we will utilize *anti*-[¹⁸F]FACBC avid tissue to confirm that the following AAT subtypes based on preliminary data are expressed at the protein level: PAT 1, LAT1, LAT2, 4F2hc, and ASCT2, LAT3 and ASCT1. We will study 8-10 samples of each recurrent prostate carcinoma in the prostate bed and 8-10 samples of disease outside the prostate bed, preferably in the same patient. We predict that one or more AAT subtypes will be relatively overexpressed by IHC in FACBC-avid carcinoma. We also predict that there will be differences in mRNA expression

based on these tissue samples between disease confined to the prostate bed and those that are extraprostatic. Based upon tissue availability we will perform IHC in the following rank priority: First: PAT 1; Second: LAT1, LAT2, 4F2hc; Third: ASCT2, LAT3 and ASCT1. This priority ranking is based on our desire to first confirm phenotypic expression of PAT1, since presence of this AAT correlated most strongly with *anti*-[¹⁸F]FACBC uptake, followed by LAT1 and LAT2 with the heterodimeric associated protein 4F2hc, and ASCT2, LAT3 and ASCT1.

C 2.1 Quantitative next-generation mRNA sequencing

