Methods. For experiments on fixed tissue RNA will be extracted at the Cancer Genomics Shared Resource (CGSR) at the Winship Cancer Institute from macrodissected 5 micron sections. The CGSR has extensive experience in preparing Total RNA from FFPE tissues [42]. FFPE RNA extraction will be performed using the Omega Biotech methodology in 96-well format on a Kingfisher FLEX Liquid Handler Robot. FFPE RNA will be quantitated by nanodrop spectrophotometry, and tested for RNA integrity and quality by Taqman analysis of the RPL13a ribosomal protein. Samples with sufficient yield (>500 ng), A_{260}/A_{280} ratio > 1.8 and RPL13a C_T values less than 31 cycles will be used for preparing sequencing libraries using the TrueScript kit (Illumina). Amplified cDNA libraries will be sonicated to an average length of 250 bp with a Covaris E-120 Adaptive Focused Acoustics Instrument. We will repair the ends of the sonicated DNA using the Illumina TrueScript protocol and generate barcoded libraries for RNA-seq analysis on an Illumina HiSeq 2000 instrument at the Southern California Genotyping Consortium at UCLA. Agilent Bioanalyzer Nanochip analysis will be performed to ensure the integrity of libraries prior to sequencing. We will obtain 60 million reads per sample of 50bp paired-end sequencing reads using the Illumina version 3 kits with three samples multiplexed per sequencing lane.

Fluorogenic quantitative RT-PCR assays will be used to confirm changes identified by RNA-seq analysis and performed in triplicate with standard SYBR-Green methodology on the I-cycler system (Bio-Rad, Hercules, CA, USA) according to published protocols with minor modifications [43]. Reaction specificity will be assessed by melting point analyses, in which single melting point peaks are required at temperatures predicted by amplicon sequence. Reactions without reverse transcription and template will serve as controls for DNA contamination and specimen carry-over. Test gene expression will be normalized to 28S ribosomal RNA and referenced to a standard RNA specimen. Relative normalized gene expression of each LAT subtype will be compared in FACBC avid versus non-avid prostate carcinoma, with statistical significance assessed by analysis of variance (ANOVA).

C 2.2 Immunohistochemistry

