Methods. Fixed tissue sections (5 μ m thickness) will be dewaxed, and steam antigen retrieval will be performed at pH 6.5 in a pressure cooker for 20 minutes [44]. Tissue sections will be incubated with primary antibodies directed against PAT 1, LAT1, LAT2, 4F2hc, and ASCT2, LAT3 and ASCT1. Sections will be deparaffinized and subjected to heat-induced epitope retrieval by steaming for 15 minutes. IHC staining will be performed at the Winship Cancer Institute Research Pathology Shared Resource using an automated (DAKO) immunohistochemistry stainer and established procedures and protocols. Optimal dilutions for all antibodies will be determined empirically using archived sections from prostatectomies and blocking reagents recommended by the manufacturers. Immunohistochemical reactions will be developed with diaminobenzidine as the chromogenic peroxidase substrate. Sections will be counterstained with hematoxylin after immunohistochemistry. Specificity will be verified by negative control reactions without primary antibody. Intensity of the various immunohistochemical stains were scored blindly by a board-certified pathologist as follows; 0-

negative, 1+ (weak), 2+ (intermediate) and 3+ (strong). The expression of these markers will be correlated with FACBC uptake by ANOVA testing

C 2.3 RNA-Seq Results and Imaging Findings

RNA-Seq sequencing reads produced from the Illumina HiSeq 2000 will be mapped to the human reference genome (hg19) using Bowtie [45] and fragment reads per kilobase (FRPK) calculated using TopHat [46]. Only uniquely mapped reads will be retained for analysis. Relative changes in mRNA expression will be computed using Cufflinks and Cuffdiff [47] in a locally installed Galaxy bioinformatics environment [48, 49] deployed by the [name] laboratory.

D. Subject recruitment:

All patients will be recruited from the Emory Healthcare (Drs. [name], [name], [name] and [name]), Urology and Radiation Oncology clinics per the inclusion and exclusion criteria below.

Inclusion Criteria:

1. Patients must be 18 years of age or older.
2. Patients will have been originally diagnosed with localized (Stage T1c, T2, or T3) prostate carcinoma and have undergone what was considered definitive non-prostatectomy therapy for localized disease.

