Depending on the normality of data distribution, t-test or Wilcoxon rank sum test will be conducted to compare the mRNA differences, genomic differences in gene expression, alternative splicing, indels and single base mutations between prostate carcinoma recurrent in the prostate bed and extraprostatic samples. Analysis of variance (ANOVA) will be used to compare the IHC staining of protein levels between the different categories of FACBC uptake. Tukey pairwise comparison will be further conducted when the overall comparison with ANOVA

Version 9-23-13

Version 11-6-13

Version 11-11-14

Version 12-4-14

is significant at the significance level of 0.05. Pearson/Spearman correlation coefficients will be estimated to measure the associations: 1) between mRNA levels of candidate AAT genes and FACBC uptake; 2) between mRNA differences and quantifiable imaging biomarker data such as SUV for *anti*-[¹⁸F]FACBC PET-CT and ADC for MR. Multivariate analyses will further be conducted, in which general linear model (GLM) will be employed to assess the adjusted relationships mentioned above after adjusting for the other covariates.

Sample size and power calculation

The sample size of this study is 25 patients. The power calculation is based on the comparison of mRNA differences between the prostate bed and extraprostatic samples using two sided t-test. At the significance level of 0.05, the sample size of 25 will achieve a power of at least 80% to detect one standard deviation or higher difference in mRNA difference between the two groups of samples.

F. Adverse Event Reporting

An adverse event is defined as any untoward medical occurrence associated with the use of a drug in humans whether or not considered drug-related

A significant shift from baseline which can be attributable to the radiotracer injection and not the patient's medical condition will be considered an unexpected AE. An event greater than 7 days post scan will not be considered an AE since 95% of ligand is eliminated by 7days.

The National Cancer Institute's Common Terminology Criteria for Adverse Events (CTCAE) Version 4.03 (June 14, 2010) will be used as a guide address potential AEs subject to limitations above and medical and scientific judgment as to plausibility of such criteria in a diagnostic radiotracer study.

Adverse Event Reporting

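### Aim 2 intends a same-patient comparison, but E2.0 does not name a paired analysis; separately, it states no multiplicity rule for the RNA-seq-wide tests

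*Combined protocol and SAP*

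**What the plan says.** **Design.** Aim 2 expects "at least 8-10 patients in whom this comparison can be directly made will be available for analysis". The Rationale for Aim 2 and Sub-aim 2a values the trial as a chance to "obtain both prostatic and extraprostatic tissue from the same patient in order to test these hypotheses using the patient as his own control". Section C2.0 plans 8-10 bed samples and "8-10 samples of disease outside the prostate bed, preferably in the same patient", so pairing is preferred but not required.

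**Analysis.** Section E2.0, under Aim 2 and Sub-aim 2a, chooses the test by the normality of the data: "t-test or Wilcoxon rank sum test will be conducted to compare the mRNA differences, genomic differences in gene expression, alternative splicing, indels", and goes on to single base mutations. It adds a GLM with unnamed covariates. Tukey comparisons follow the IHC ANOVA only. The mRNA differences are then correlated with SUV and ADC.

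**Other RNA statements.** Section C 2.3 says "Relative changes in mRNA expression will be computed using Cufflinks and Cuffdiff". Section C 2.1 says "Fluorogenic quantitative RT-PCR assays will be used to confirm changes identified by RNA-seq analysis". Neither gives a q-value, an FDR or another threshold for calling a gene different.

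**Power.** The sample size section states: "At the significance level of 0.05, the sample size of 25 will achieve a power of at least 80% to detect one standard deviation". The test there is a two-sided t-test, again without a word on pairing.

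**The concern.** There are two separate gaps, and they act in opposite directions.

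1. **Pairing.** When both samples come from one man, variation between men cancels out of the within-man difference. An independent-groups test leaves that variation in the error term. If the two sites are positively correlated, the test rejects too rarely and loses power on a very small sample.
2. **Multiplicity.** RNA-seq yields a very large family of tests over expression, splicing, indels and mutations. With no stated error rate, a reader cannot tell how many entries in the gene list are chance. RT-PCR would then have to sort an unknown share of false leads, and the correlations with SUV and ADC would start from an undefined list.

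In addition, two routes to significance are described (the E2.0 tests and Cuffdiff) and neither is named as deciding.

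**Working it through.** **The plan's own figure.** Noncentral-t power for a 1 SD difference, two-sided 0.05:

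- 25 per site, two-sample: 93.4%.
- 25 pairs: 99.8% if 1 SD is the SD of the within-man differences; 92.4% if it is the SD of single samples and the correlation is 0.
- 25 samples in total, 12 against 13: 66.7%.
- 10 pairs, 1 SD of the differences: 80.3% (8 pairs 68.1%, 9 pairs 74.8%).

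So at least 80% holds for 25 per site, for 25 pairs, or for 10 pairs on the difference scale. It is in every case a figure for one comparison at 0.05. How 25 relates to the 8-10 samples per site in C2.0 is a related but separate matter.

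**Pairing.** Inputs: 8-10 pairs (Aim 2, C2.0); difference 1 SD and alpha 0.05 (sample size section); within-man correlation ρ, not in the documents, assumed 0 to 0.7. SD is 1 at each site.

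- Paired t: the SD of the differences is √(2(1−ρ)), the noncentrality is √n / √(2(1−ρ)), with n−1 df. At ρ = 0.5 the SD is √1 = 1, so the noncentrality is √8 = 2.83 for 8 pairs and √10 = 3.16 for 10.
- Two-sample t on the same pairs: it uses a variance of about 2/n for the mean difference, while the true variance is 2(1−ρ)/n. Its power and true alpha come from simulation (60,000 data sets).

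| ρ | Unpaired t power, 8-10 pairs | Paired t power, 8-10 pairs | True alpha, unpaired t (9 pairs) |
|---|---|---|---|
| 0 | 46-56% | 41-51% | 5.0% |
| 0.1 | 46-57% | 44-56% | 3.9% |
| 0.3 | 46-57% | 54-66% | 2.2% |
| 0.5 | 46-58% | 68-80% | 1.0% |
| 0.7 | 46-61% | 88-95% | 0.25% |

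The rank sum test at ρ = 0.5 has power 37% (8 pairs) and 53% (10 pairs); the signed-rank test has 61% and 78%.

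**Multiplicity.** The number of genes tested is not in the documents; 10,000-25,000 null genes are assumed, and the list is assumed to be selected by raw p<0.05.

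- Valid test: 0.05 × 10,000 = 500; 0.05 × 25,000 = 1,250.
- Unpaired test at ρ = 0.5, true alpha about 1%: 0.01 × 10,000 = 100; 0.01 × 25,000 = 250.

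**What FDR control would leave.** Simulation with 9 complete pairs, 20,000 independent genes, 1,000 of them truly different by 1 SD, and Benjamini-Hochberg (BH) at 5%. True genes found:

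| ρ | Correlation pooled over genes | Gene-by-gene paired t |
|---|---|---|
| 0 | about 4 | about 0 |
| 0.3 | about 17 | about 1 |
| 0.5 | about 120 | about 7 |
| 0.7 | about 533 | about 152 |

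These counts vary somewhat from run to run.

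**The case against.** **The t-test may be meant as paired.** It is named first and is the basis of the power statement, and 10 pairs on the difference scale give 80.3%. This stands as a possibility. A reader might infer that the plan prescribes an unpaired t-test; the text does not say that. But it does not say paired either, and its named alternative is unpaired.

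**Pairing is only preferred.** This also stands: C2.0 allows some single samples. That argues for a method that uses both pairs and single samples, not for ignoring the pairs.

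**The pairing error is conservative.** True. A reader might infer that ignoring pairing inflates false positives. Under positive correlation it does the reverse, and at correlation 0-0.1 the unpaired t-test does slightly better.

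**Cuffdiff may correct for multiplicity.** What the software applies by default is outside the documents. A reader might infer that no control would operate in practice; that is not shown. What is shown is that no rule is stated. Likewise 0.05 is attached to the Tukey trigger and the power statement, not to the gene list, so the false-positive counts are conditional.

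**Extra bed-only samples could change the picture.** The counts in the Rationale suggest 25 × 25/73 = 8.6 men with both sites and 25 × 41/73 = 14.0 with bed disease only. A reader might size the problem on 9 pairs plus 14 bed-only samples, where FDR yields are higher. C2.0 plans 8-10 samples per site, so that structure applies only if more bed samples are sequenced.

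**The aim is secondary, in a preliminary trial, with RT-PCR confirmation.** This limits the severity. RT-PCR is a useful check on individual genes, but it sets no error rate for the list.

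**Conclusion.** The concern holds as two gaps in specification for a secondary aim.

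- **Pairing.** The design seeks same-patient tissue; the analysis names an independent-groups test or a t-test of unstated pairing, with no patient term. At 8-10 pairs and correlation 0.5, reading the plan as unpaired costs about 22 points of power (46-58% against 68-80%). The loss is larger at 0.7 and absent at 0-0.1. The correlation is an assumption throughout.
- **Multiplicity.** No error-rate rule covers the RNA-seq-wide tests, and no analysis is named as deciding. The 500-1,250 false positives (100-250 for the unpaired test at correlation 0.5) rest on an assumed gene count and on selection by raw p<0.05.

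The gaps in the text do not depend on these assumptions; only their size does. It should be fixed, because the trial's only power calculation rests on this comparison and its results feed the SUV and ADC correlations. No Aim 1 result depends on it.

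**What to change.** In E2.0, replace the sentence on the t-test and rank sum test with wording such as:

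> For each gene, log expression will be compared between sites in a model with site as fixed effect and patient as block or random effect, so that pairs and any single samples both contribute. Genes will be declared different by Benjamini-Hochberg FDR at 5%. This analysis decides significance; Cuffdiff output is supportive.

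If Cuffdiff is to decide instead, say so and state its threshold and how it handles patient. Say also how the within-patient correlation is estimated; pooling it over genes found more true genes in the simulation above. Add to the sample size section that the stated power is for one comparison at 0.05.

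The minimum is to state that the t-test is paired, replace rank sum by signed-rank on complete pairs, and state the FDR rule. Signed-rank then has a limit. Its smallest p is 2/2^n, which is 0.0078 for 8 pairs and 0.0020 for 10. BH at 5% over 20,000 genes needs k ≥ p × 20,000/0.05 genes at that p, about 3,100 for 8 pairs and 780 for 10.

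**Cost.** SAP wording and standard software, with no change to any patient procedure. C1.7 and C2.0 place the RNA work at the end of the study or once enough tissue is collected, so the rule can be set beforehand. The real price is a short gene list: at C2.0's numbers and low correlation, few or no 1 SD genes would survive FDR. The plan should say so and label unadjusted results exploratory. Small-sample df methods and exact tests for present/absent mutations are optional detail.

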3) For *anti*-3-¹⁸F]FACBC, uptake will be defined according to the following criteria in relation to background structures: mild (above blood pool but less than marrow), moderate (above or equal to marrow but less than liver), and intense (equal to or above liver). Visual analysis will be aided by quantitative criteria of SUV_{max} lesion/SUV_{mean} background. Maximum and mean SUV of each focus of abnormal uptake as well as background structures including liver, marrow at L3, aorta, and bladder will be recorded. For prostate beds as well as extra-prostatic sites such as lymph nodes and bone, abnormal moderate or intense focal uptake over background marrow which persist from early to delayed images will be considered prospectively positive. These criteria were used to analyze data in our study of *anti*-¹⁸F]FACBC in recurrent disease [40].

4) Confidence in interpretation for disease within the prostate bed and outside the bed will be recorded with the following scale on a per patient basis and any all recordable lymph nodes: 1- definitively negative; 2 -probably negative; 3 - indeterminate; 4 - probably positive; 5 – definitively positive.

5) In summary, we will record both visual and semi-quantitative analysis of the prostate bed, positive lymph nodes (greater than blood pool), and other structures such as skeletal foci on early and delayed time frames. We will use maximum and mean SUV as well as standard bidimensional size measurements. We will also record similar measurements on background structures such that we may derive uptake ratios.

C1.5 Image Analysis of MR

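### Sub-aim 2a tests the 0–3 staining score across uptake categories with an omnibus ANOVA, setting aside the order of uptake and the lesion SUV already recorded

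*Combined protocol and SAP*

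**What the plan says.** All places are in the combined protocol and SAP.

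- **Outcome.** C2.2 (Immunohistochemistry) has a blinded pathologist score stain intensity from 0 to 3: "negative, 1+ (weak), 2+ (intermediate) and 3+ (strong").
- **Test.** E2.0 (Secondary Aims): "Analysis of variance (ANOVA) will be used to compare the IHC staining of protein levels between the different categories of FACBC uptake". Then: "Tukey pairwise comparison will be further conducted when the overall comparison with ANOVA" "is significant at the significance level of 0.05". C2.2 words the same analysis differently: "The expression of these markers will be correlated with FACBC uptake by ANOVA testing".
- **Uptake categories.** E2.0 does not define them. C1.4 grades uptake as "mild (above blood pool but less than marrow), moderate (above or equal to marrow but less than liver"), with intense at or above liver, and counts only moderate or intense focal uptake that persists as positive. C2.1 uses two groups for RT-PCR: "Relative normalized gene expression of each LAT subtype will be compared in FACBC avid versus non-avid prostate carcinoma".
- **Tissue.** C2.0 will use FACBC-"avid tissue to confirm that the following AAT subtypes based on preliminary data are expressed at the protein level". It plans 8–10 samples from the prostate bed and 8–10 from outside it, preferably from the same men, and predicts relative overexpression of at least one transporter in avid carcinoma.
- **Continuous uptake.** C1.4 records maximum and mean SUV for each abnormal focus, on early and delayed images.
- **Rank correlation.** E2.0 lists Pearson/Spearman coefficients for mRNA against uptake and for mRNA differences against SUV and ADC. It lists none for the staining score.

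**The concern.** The question is whether more transporter protein goes with more uptake. A one-way F test asks a different question: whether any category mean differs from any other, in whatever direction or order. Some of its power goes to patterns that nobody predicts. Cutting SUV into two or three visual grades loses further information.

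With 16–20 samples there is little to spare, and lower-priority proteins may have fewer because staining depends on available tissue. A real association could be missed when a better-aimed analysis of the same data was available. E2.0 already names such an analysis for the parallel mRNA question.

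**Working it through.** **The plan's own figure.** There is none to reproduce. The only power statement (E2.0: 25 patients, at least 80% for a one-SD difference) concerns mRNA by site with a t-test, and says nothing about staining.

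**Inputs from the documents.** Samples: 8 + 8 = 16 to 10 + 10 = 20, midpoint 18. Score: four ordered levels. Groups: three under C1.4, or two under the avid/non-avid split. Two-sided alpha: 0.05.

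**Inputs assumed.** Strength and shape of the relation, score distribution and group sizes. The documents give none of these for staining.

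**Step 1. What the F test uses.** With k groups, N samples, group means ȳ_g and overall mean ȳ,

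F = [Σ n_g(ȳ_g − ȳ)² / (k − 1)] / [ΣΣ(y_gi − ȳ_g)² / (N − k)].

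With k = 3 and N = 18 the degrees of freedom are 2 and 15. Relabelling mild, moderate and intense in any order leaves F unchanged, so the order of uptake is not used. The score enters as the number 0, 1, 2 or 3, so its order is used, with equal spacing imposed.

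**Step 2. Keep the categories and use a trend test.** Scores were simulated from a proportional-odds model (20,000 runs per setting, log-odds shift of 1.5 to 4 between extreme groups, independent samples).

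| Setting | Trend test minus ANOVA, power points |
|---|---|
| Three balanced groups, linear trend, N = 16–20 | about 5 to 13 |
| Groups of 3/6/9 | about 2 to 9 |
| Groups of 2/6/10 or 2/6/12 | about 0 to 8 |
| Two groups | −3 to +1 |
| Only the top group differs | −7 to +6 |

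Example: 6/6/6, uniform scores, shift 2.5. ANOVA 50%, Spearman on category 62%, a gain of 12 points. ANOVA's type I error on the 0–3 score was 4.3–5.9%.

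**Step 3. Use SUV itself.** A latent staining variable was correlated 0.5 to 0.7 with continuous uptake and cut to 0–3. Spearman used the continuous uptake; ANOVA used uptake cut into two or three groups.

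- 18 samples, two or three groups, with or without within-patient correlation: Spearman gains about 14–27 points. Type I error was 5–7% for Spearman and 4–6% for ANOVA.
- 18 samples, correlation 0.6, two equal groups: ANOVA 50%, Spearman 66%, a gain of 16 points.
- A separate run over 16, 18 and 20 independent samples gave 14–25 points for three groups, 12–17 for two equal groups and 17–31 for a 25/75 split.

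**Step 4. Two samples from one man.** Permuting strictly within patient is one way to respect pairing. With nine pairs and within-patient correlation 0 to 0.5, it had 7–25% power on categories (ANOVA 34–78%) and 7–43% on continuous uptake (ANOVA 25–76%). On categories it rejected a true null only 0.5–0.9% of the time. It discards the between-patient information and is unsuitable here.

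**The case against.** - **ANOVA ignores both orderings.** A reader might infer this. It is true only of the uptake groups. The score's order is used with equal spacing, which cost no visible power and did not inflate type I error. The planned test is not invalid.
- **The plan loses about 10 points of power.** This is tempting but needs three roughly balanced groups and a monotone effect. The categories are undefined, and using avid tissue makes a two-group comparison or a nearly empty low group plausible. A category trend test then gains little or nothing. This objection stands against a category trend test but not against SUV, which still gained with two groups.
- **A non-monotone relation favours ANOVA.** This stands. With 6/6/6 and only the middle group shifted by 2, ANOVA had 44% power and Spearman 3%. The plan predicts no such pattern.
- **Pairing is not free.** This stands in part. The simulated gains are for ordinary Spearman, not a cluster-adjusted version, and cluster methods are approximate with perhaps 8–10 men.
- **The general linear model in E2.0 may cover it.** Possibly, but that sentence names neither an ordinal model nor SUV as predictor of staining.
- **C2.2 and E2.0 contradict each other.** They do not: both name ANOVA. C2.2 merely calls it a correlation.
- **It is a tissue-permitting sub-aim of a preliminary trial with no power claimed.** True, and the reason the point is minor.

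**Conclusion.** The point holds as an improvement to the analysis. As written, the main staining test leaves the order of uptake unused and replaces a recorded continuous measure with undefined categories, in 16–20 samples and against a directional prediction.

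If the relation is monotone with latent correlation 0.5 to 0.7, Spearman on SUV gains roughly 14–27 points of power with 18 samples, whether ANOVA would have used two or three groups. Those figures rest wholly on assumed effects and should not be read as the plan's known loss. If staining were restricted to avid tissue, the narrower SUV range could also lower the power of either test. Aim 1 is unaffected.

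**What to change.** 1. In E2.0, make Spearman correlation of the staining score with lesion SUV (or ordinal logistic regression on SUV) the main test for Sub-aim 2a, in line with the mRNA analysis.
2. Name one SUV measure in advance (maximum or mean, early or delayed), and state that it will be measured at every sampled site, including any without abnormal uptake.
3. Define the uptake categories, use them for description only, and drop the Tukey step.
4. Where a man gives two samples, use a method that keeps between-patient information, such as a patient-level cluster bootstrap or cluster-robust standard errors, and acknowledge the small number of men. Do not permute strictly within patient.
5. Reword C2.2 to match E2.0.

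The cost is a wording change in two sections and, at most, an SUV reading at sampled sites not otherwise measured. No extra patients, tissue or staining is needed. The price is lower power if the relation turns out to be non-monotone; the descriptive display by category would help reveal that.
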